4.3. Participant Withdrawal Criteria

Participants have the right to withdraw from the trial at any time for any reason without penalty. The Investigator also has the right to withdraw participants from the trial if they believe it is in the best interest of the participant, or if the participant is uncooperative or noncompliant.

Participation in this clinical trial may be discontinued for any of the following reasons:

- The participant withdraws consent or request discontinuation for any reason
- Any adverse event, illness, medical condition, or severe laboratory abnormality which indicates to the Investigator that continuation in the trial is not in the best interest of the participant
- Failure to comply with protocol requirements or trial-related procedures
- Pregnancy
- Trial terminated by the Sponsor

Should a participant decide to withdraw, all efforts will be made to complete and report the observations as thoroughly as possible, particularly the examinations outlined in the ET visit.

The Investigator or designee should contact the participant to determine, as accurately as possible, the primary reason for their withdrawal.

A complete final evaluation at the time of the participant's withdrawal should be made with an explanation of why the participant is withdrawing from the trial. If the reason for removal of a participant is an adverse event (AE) or an abnormal laboratory test result, the principal specific event or test must be recorded. If a participant withdraws from the trial, they may request destruction of any samples taken and not tested, and the Investigator must document this in the site trial records.

A participant will be considered lost to follow up if they repeatedly fail to return for scheduled visits and are unable to be contacted by the clinical trial center. Before a participant is considered lost to follow up, the Investigator (or designee) must make every effort to regain contact with the participant (where possible, 3 telephone calls, and if necessary, a certified letter to the participant's last known mailing address or local equivalent methods). These attempts should be documented in the participant's medical record.

5. STUDY INTERVENTION(S) AND CONCOMITANT THERAPY

5.1. Description of Study Drug

The ASN008 topical gel formulations are composed of the active pharmaceutical ingredient (ASN008), propylene glycol, Poloxamer 407, methylparaben (preservative), propylparaben (preservative), and sterile water. Three gel formulations in strengths of 1.25%, 2.5%, and 5.0% have been manufactured in support of this clinical trial.

Additional information for ASN008 topical gel and vehicle formulations is provided in the IB.

5.2. Concomitant Medications

All medications (including over the counter products including pills creams and topical treatments, vitamins, herbal/natural products [including cannabidiol], and antacids) taken within the 4 weeks prior to screening and throughout the trial must be recorded.

All past and current medications taken for AD (topical and systemic) will be documented as medication history for AD. The duration of the treatment and the reason for discontinuation will be documented.

Medication entries may be captured as generic names. Entries should include the following information if known: dose, unit, frequency of administration, route of administration, start date, discontinuation date, and indication. If the medication is discontinued or the dosage is changed, these details must be recorded.

5.2.1. Required Concomitant Therapy

Participants should apply a non-prescription emollient of their choice (participant's choice, excluding those containing hydrocortisone, urea, antihistamines, anesthetics, antibiotics, cannabidiol, or Vitamin C) daily or BID to any untreated lesions and all dry skin areas of the body for at least 7 days prior to Day 1 until the End of Study (Week 8) or ET visit. The emollient should be applied to any area needed except for the AD skin lesion(s) treated with the IP during the treatment period. On the day of scheduled visits, participants should not apply emollients before their scheduled visit time.

Every effort must be made to keep the same emollient throughout the trial. The commercial name of the selected emollient(s) must be recorded in the source document and the eCRF. No other products can be applied to the lesions during the trial. Emollient use should be recorded daily in the participant diary.

5.2.2. Permitted Therapies

The following therapies are permitted:

- Intranasal corticosteroids and inhaled corticosteroids for stable medical conditions were allowed. Eye and ear drops containing corticosteroids were allowed.
- Use of sunscreen products on non-treated areas (except those containing Vitamin C), and protective apparel are recommended when exposure cannot be avoided.

Drugs that were known to moderately inhibit CYP3A4 and CYP2D6 should be used with caution, and only following approval by the Medical Monitor. These drugs include amprenavir, aprepitant, atazanavir, ciprofloxacin, crizotinib, diltiazem, erythromycin, fluconazole, fosamprenavir, imatinib, verapamil, cinacalcet, duloxetine, and terbinafine.

5.2.3. Prohibited Therapies

Table 6 lists prohibited medications not to be used from the defined washout periods before the first application of trial treatment (Day 1) through timepoint specified (end of treatment period or end of trial). Participants who start a prohibited medication or therapy as a treatment for AD or other reasons during the trial will be withdrawn from trial treatment and the medication must be recorded in the eCRFs.

For the purposes of this study, cannabis is considered a systemic treatment that may impact AD due to its effect on itch, potentially interrupting the itch/scratch cycle. As such, participants should not use any form of cannabis (e.g., inhaled, edible, topical, tincture) either medicinally or recreationally during the study.

Anti-histamines should be discontinued for at least 1 week ahead of Day 1, through the end of the treatment period.

Table 6 Prohibited Therapies or Procedures

Prohibited medications, products, and procedures	Minimal Interval Prior to First IP Dose	Timepoint Therapy may be Restarted
Any marketed or investigational biological agent	12 weeks or 5 half-lives (whichever is longer)	After Day 56
Dupilumab	12 weeks	After Day 56
Nonbiological IP or device	4 weeks (or 8 weeks if $t_{1/2} > 15$ days)	After Day 56
Drug or substance known to be strong inhibitor or inducer of CYP3A4 or CYP2D6 (e.g., boceprevir, clarithromycin, conivaptan, grapefruit juice, indinavir, itraconazole, ketoconazole, lopinavir/ritonavir, mibefradil, nefazodone, nelfinavir, posaconazole, ritonavir, saquinavir, telaprevir, telithromycin, voriconazole, bupropion, fluoxetine, paroxetine, quinidine)	4 weeks	After Day 56
JAK inhibitor (oral or topical)	4 weeks	After Day 56
Systemic treatments (other than biologics) that could have affected AD (e.g., retinoids, calcineurin inhibitors, methotrexate, cyclosporine, hydroxycarbamide [hydroxyurea], azathioprine, oral/injectable corticosteroids)	4 weeks	After Day 56

Prohibited medications, products, and procedures	Minimal Interval Prior to First IP Dose	Timepoint Therapy may be Restarted
Note: Intranasal corticosteroids and inhaled corticosteroids for stable medical conditions were allowed. Eye and ear drops containing corticosteroids were allowed.		
PUVA treatment, UV-B phototherapy (including tanning beds) or excimer laser, excessive sun exposure or had used tanning booths	4 weeks	After Day 56
Topical medicated treatment that could have affected AD including, but not limited to, topical corticosteroids, crisaborole and any other topical phosphodiesterase-4 inhibitor, calcineurin inhibitors, tars, bleach, antimicrobials, medical devices, and bleach or oatmeal baths	2 weeks	After Day 56
Systemic antibiotics	2 weeks	After Day 56
Topical antibiotics	1 week	After Day 56
Antihistamine	1 week	After Day 28
Topical products containing urea	1 week	After Day 28
Hydroxyzine and diphenhydramine	1 week	After Day 28
Doxepin	1 week	After Day 28

AD=atopic dermatitis; CYP=cytochrome P450; IP=investigational product; JAK=Janus kinase; PUVA=psoralen-UV-A; $t_{1/2}$ =half-life; UV=ultraviolet.

5.3. Treatment Compliance

Treatment compliance will be monitored at each visit. Adherence to treatment will be assessed by direct questioning, review of the participant's dosing diary, and by maintaining adequate trial product dispensing and return records. Any deviation from the prescribed dosage regimen will be recorded in the source document and eCRF.

Participants who are significantly noncompliant with treatment (ie, administration of <80% of the expected treatments) based on IP accountability will be counseled and could be discontinued from the trial, at the discretion of the Investigator, following consultation with the Sponsor. A participant will also be considered significantly noncompliant if he or she intentionally or repeatedly takes more than the prescribed amount of trial product in the same time frame, as judged by the Investigator.

5.4. Study Restrictions

Participants should abstain from taking a bath/shower or swimming within 2 hours following each treatment application. If there are lesions on the hands, participants should abstain from washing their hands within 2 hours following each treatment application.

Participants should abstain from physical activity that could cause significant sweating within 2 hours following each treatment application.

Participants should be informed not to wear tight clothing on treated areas and to avoid touching the treated area(s) until areas of application were dry.

Participants should avoid eye contact with the trial products.

Participants should not consume grapefruit, grapefruit juice, or any grapefruit containing product within 4 weeks prior to Day 1 and throughout the entire trial duration.

Participants should avoid excessive sun exposure and refrain from sunbathing, receiving UV phototherapy or using a tanning booth during the study.

Participants should be informed not to change emollients during the study and that on the day of scheduled visits, emollients should not be applied before the scheduled visit time.

5.5. Assignment to Study Intervention

At the investigational site, each screened participant will be assigned a participant identifier number during screening that will be used on all participant documentation.

Participants will be randomized in a 1:1:1:1 ratio to receive either ASN008 gel at 1.25%, 2.5%, or 5.0%, or vehicle BID. Randomization will occur as part of the Randomization visit. The Randomization visit will be conducted remotely via phone once all screening assessments have been completed and the results of those assessments are determined to be in line with the trial entry criteria (i.e., based on central read ECG, central laboratory results, and all clinical outcome assessments and patient-reported outcome assessments). During this remote check-in, study staff will verify the participant's desire to continue in the trial, record any AEs, assess concomitant medications, and confirm that non-prescription emollient has been (or will be) used consistently for at least 7 days prior to Day 1. Study staff will then acquire a randomization number for eligible participants, which will prompt shipment of investigational product to the study site. The interval between the Randomization Visit and Day 1 Visit should allow enough time for the investigational product to arrive at the study site (i.e., approximately 1 week).

The randomization list will be generated using a validated software. The master randomization list will be kept secured until the trial blind is broken at the end of trial. This list will be uploaded into an Interactive Web Response System (IWRS). The Investigator or designee will be able to acquire a randomization number for eligible participants by connecting to the IWRS.

Further guidance and information can be obtained in the Pharmacy Manual.

5.6. Blinding

This trial will be double-blinded. At all times, treatment and randomization information will be kept confidential and will not be released to the Sponsor's trial team until database lock is completed and all safety data has been cleaned and monitored. Investigators, participants, and clinical staff will remain blinded throughout the trial.

Blinding codes should only be broken in emergency situations for reasons of participant safety. If unblinding the treatment assignment for a participant is necessary due to a medical emergency (an unexpected serious adverse event [SAE] per product's safety profile) and other significant

medical situations such as pregnancy, the Investigator can make the decision to unblind the treatment assignment if knowing the treatment assignment will help the treatment decision of the particular AE. When the blind for a participant has been broken, the reason must be fully documented in the source document and eCRF. Whenever possible, the Investigator should contact the Sponsor or its designee before breaking the blind. If the blind is broken, the Investigator should promptly inform the medical monitor. Documentation of breaking the blind should be recorded with the date/time and reason why the blind was broken, and the names of the personnel involved.

Emergency unblinding details are provided in the Pharmacy Manual.

The participant for whom the blind has been broken will be discontinued from the trial and undergo the ET procedures. In cases where there are ethical reasons to have the participant remain in the trial, the Investigator must obtain specific approval from the Sponsor or its designee for continuation. The primary reason for discontinuation (the event or condition which led to the unblinding) will be recorded.

6. STUDY DRUG MATERIALS AND MANAGEMENT

6.1. Study Drug Administration

The topical gel should be applied to all AD lesions (except scalp, axillae, groin, genitals, and folds), with a maximum treated area of approximately 20% BSA. If new lesions on the soles of the feet appeared after Day 1 and initiation of treatment, then these lesions should be excluded from the BSA of treated area (should not be treated).

Participants should apply the gel as a thin layer using the fingertip unit (FTU) where a thin layer corresponded to approximately 2 mg/cm². A FTU is the amount of gel expressed from a tube applied from the distal skin-crease to the tip of the palmar aspect of the index finger and 1 FTU covers approximately 286 cm² (approximately 1.5% BSA) ([Long 1991](#)). The number of FTUs required to cover the treated area should be calculated for each participant and recorded at Day 1 and Day 15. Participants should be informed of how many FTUs they should apply on their AD lesions.

The topical gel will be applied to completely cover the lesions with a thin glistening layer. The gel may be applied on superficial abraded skin, but deeper wounds should be avoided. All original areas of involvement at Day 1 (even in the event of lesions clearing), and any new lesions (up to a maximum treated area of approximately 20% BSA) should be treated until Week 4. If new lesions appeared after Day 1, the new surface area to be treated (up to a maximum treated area of approximately 20% BSA) should be evaluated at every visit, and if applicable, the number of FTUs to be applied on AD lesions should be calculated and recorded. If new lesions on the soles of the feet appeared after Day 1 and initiation of treatment, then these lesions are excluded from the BSA of treated area (should not be treated).

The study treatment will be applied twice daily (except on Day 28), at approximately the same times each day; the date and time of each application will be recorded in the eDiary. It is recommended that the application times be approximately 12 hours apart (± 2 hours). Participants should not shower or perform activities that may cause sweating for 2 hours post-application. Participants with AD lesions on hands should avoid washing their hands for approximately 2 hours post drug application. Participants without AD lesions on hands should wash their hands after treatment application.

If an application is missed participants should apply the study treatment as soon as they remember on the same day. However, if it is the next day, the missed application should be skipped and the next application should be applied as normal.

Participants will be trained on how to apply the study treatment on Day 1 with reminders given at each subsequent visit, which will be documented. Participants will apply their first dose (on Day 1) and their last dose (on Day 28) at the study site. When participants are dosed at the study site, they will self-apply the treatment under the direction and supervision of delegated study staff; the date and time of the application will be recorded by the site staff on the eCRF.

Participants are not to receive study treatment for more than 28 days.

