Using analysis outlined above for the primary endpoint, N=24/cohort will give 80% power to detect a standardized effect of 0.72 with 2-sided significance level of 0.1 (28.8% improvement over placebo in percent change from baseline in pruritus, assuming SD = 40%).

Table 2 Schedule of Events

Study Visits	Screening (up to D-28)	Randomization ^a (phone)	Treatment Period					Follow-up/ET (Day 56/Week 8)
			D1	D8 (Week 1)	D15 (Week 2)	D22 (Week 3)	D28 (Week 4)	
Window (days)			0 days	±1 day	±2 days	±2 days	-2 days	±2 days
Informed consent	X							
Demographics	X							
Medical and surgical history	X		X					
Inclusion-exclusion criteria	X		X					
Pregnancy test (WOCBP only)	Serum		urine	urine	urine	urine	urine	urine
Clinical laboratory tests (biochemistry, hematology, urinalysis)	X		X		X		X	X
Body weight and height, BMI ^b	X		X		X		X	X
Serology (HIV, HBV, HCV)	X							
Physical examination	X		X		brief		X	brief
Vital signs	X		X	X	X	X	X	X
Electrocardiogram (12-lead, central reading)	X ^c		X ^d		X		X ^d	X ^e
vIGA	X		X		X		X	X
BSA (excluding palms, scalp, axillae, groin, genitals, and folds)	X		X		X		X	X
EASI	X		X		X		X	X
5-D pruritus scale			X		X		X	X
DLQI			X		X		X	X
POEM			X		X		X	X
Pruritus NRS ^f	X		X	X	X	X	X	
Randomization		X						
Investigational Product Application at study site			X				X	
Investigational Product BID Application Daily ^g			X				X ^g	
Participant Daily e-Diary ^h			X				X	
Investigational product distribution			X	X	X	X		
Collection of investigational product				X	X	X	X	X ^e
Verification of daily diary				X	X	X	X	
Emollient use	-7 days	X ^a	X				X	
Local tolerability assessments			X	X	X	X	X	X
PK samples collection							See Table 3	
Concomitant medication	X	X	X	X	X	X	X	X
Adverse events evaluation	X	X	X					X

BID=twice daily; BMI=body mass index; BSA=body surface area; D=day; DLQI=Dermatology Life Quality Index; EASI=Eczema Area and Severity Index; ECG=electrocardiogram; ET=early termination; HBV=hepatitis B virus; HCV=hepatitis C virus; HIV=human immunodeficiency virus; NRS=numerical rating scale; PK=pharmacokinetics; POEM =Patient-Oriented Eczema Measure; vIGA= Validated Investigator Global Assessment; WOCBP=women of childbearing potential.

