Note: In general, non-invasive procedures should be completed prior to invasive procedures. Unless otherwise specified, the study assessments scheduled during the study visits will be performed before the study product application. If assessments are scheduled for the same nominal time, then the assessments should occur in the following order, when possible: vital signs, 12-lead ECG, local tolerability, pruritus NRS, and blood draw for PK evaluation.

^a The Randomization visit will be conducted remotely via phone after all screening assessments have been completed and the results of those assessments are determined to be in line with the trial entry criteria (i.e., based on central read ECG, central laboratory results, and all clinical outcome assessments and patient-reported outcome assessments). During

this remote check-in, study staff will verify the participant's desire to continue in the trial, record any adverse events, assess concomitant medications, and confirm that non-prescription emollient has been (or will be) used consistently for at least 7 days prior to Day 1. Study staff will then acquire a randomization number for eligible participants, which will prompt shipment of investigational product to the study site. The interval between the Randomization Visit and Day 1 Visit should allow enough time for the investigational product to arrive at the study site (i.e., approximately 1 week).

^b Height will be measured only at screening and the same value will be used for BMI calculation at other visits.

^c If participant has clinically significant 12-lead ECG abnormalities (per Investigator) or QTcF >450 ms, abnormal ECG may be repeated once. For participants with QTcF >450 ms on initial ECG, the mean of the 2 QTcF assessments will determine eligibility.

^d On Day 1 and Day 28, ECGs will be time matched with PK sample collection and will be performed at time 0 (pre-dose, within 1 hour of dosing), 1 (± 15 min), 2 (± 30 min), and 4 (± 1 hour) hours post-dose. The ECG should be performed prior to the PK sample collection.

^e ET only.

^f Hourly starting immediately post dose until bedtime on Day 1 only.

^g Should not be applied to palms, scalp, axillae, groin, genitals, or folds. The last dose of investigational product should be applied during the Day 28 study visit; participants are not to receive study treatment for more than 28 days.

^h Participant will complete daily e-diary onsite during visit if not already completed.

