7.5. Body Surface Area Involvement of Atopic Dermatitis

The overall BSA affected by AD (total BSA) will be evaluated (from 0% to 100%) at the visits specified in [Table 2](#). The palmar surface of one hand represents 1% of participant's total BSA. In addition, at the screening and Day 1 visits, the BSA will be evaluated to verify each participant's eligibility, but excluding palms, scalp, axillae, groin, genitals, and folds. In addition, the BSA of treated area (include active, cleared, and new lesions) will be calculated at the visits specified in [Table 2](#). The BSA of treated area will be used to calculate the number of FTUs to be applied by participants on AD lesions (except on scalp, axillae, groin, and genitals, and folds), with a maximum treated area of approximately 20% BSA. If new lesions on the soles of the feet appear after Day 1 and initiation of treatment, then these lesions should be excluded from the BSA of treated area (should not be treated).

To be eligible, participants must have a BSA (excluding palms, scalp, axillae, groin, genitals, and folds) of 1-20% at Day 1 visit. In addition, participants with presence of AD on soles at screening or Day 1 and participants with a ratio of BSA of intended area over total BSA of less than 80% on Day 1 will be excluded.

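### Protocol Table 2 footnote g bars gel from palms, but Sections 6.1 and 7.5 list the untreated sites without palms, so a palm lesion is treated under one instruction and untreated under the other

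*Protocol*

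**What the plan says.** Two lists of untreated sites are in force.

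The list with palms is in Protocol Table 2, footnote g, attached to the daily application row: "Should not be applied to palms, scalp, axillae, groin, genitals, or folds". The SAP's schedule of events repeats that footnote. The Table 2 row for body surface area also leaves palms out, being headed "BSA (excluding palms, scalp, axillae, groin, genitals, and folds". So does the eligibility rule in Protocol Section 7.5: "To be eligible, participants must have a BSA (excluding palms, scalp, axillae, groin, genitals, and folds) of 1-20% at Day 1 visit".

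The list without palms is in Protocol Section 6.1: "The topical gel should be applied to all AD lesions (except scalp, axillae, groin, genitals, and folds". Section 7.5 uses the same list for the treated area, which sets the "number of FTUs to be applied by participants on AD lesions (except on scalp, axillae, groin, and genitals, and folds". Section 7.5 therefore uses both lists.

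Soles are handled separately. Sections 6.1 and 7.5 say that sole lesions appearing after treatment starts are not to be treated. Section 7.5 also excludes participants with sole lesions at screening or Day 1. Footnote g does not mention soles.

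**The concern.** Apart from palms, footnote g and Section 6.1 name the same sites, so a palm lesion is the case on which they give opposite instructions. Several things depend on the answer:

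- the treated area, and so the FTUs that each participant is told to apply;
- the sites scored for local tolerability, because Section 8.1.6 scores each treated lesion;
- the per-protocol amount against which Section 8.2.8 defines overdose;
- where emollient goes, because Section 3.2.1 keeps it off areas that received gel;
- possibly Day 1 eligibility, because Section 7.5 excludes participants whose intended area is less than 80% of total BSA.

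About 25 centers will apply this text. Those that rely on the schedule and those that rely on Section 6.1 may instruct similar participants differently.

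**Working it through.** The plan states no figure for this point, so there is none to reproduce. The check sets the passages side by side and then sizes the difference from the protocol's own numbers.

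**1. The lists**

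| Place | Use | Palms | New sole lesions |
|---|---|---|---|
| Table 2 footnote g; SAP copy | Where gel must not go | Untreated | Not mentioned |
| Section 6.1 | Where gel goes | Not among the exceptions | Untreated |
| Section 7.5, FTU sentences | Area that sets FTUs | Not among the exceptions | Untreated |
| Section 7.5, eligibility BSA | Day 1 entry | Excluded | Not mentioned |
| Table 2 BSA row | Scheduled BSA | Excluded | Not mentioned |

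The protocol and SAP contain no rule of precedence between these passages.

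**2. Inputs for size**

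- Section 7.5: "The palmar surface of one hand represents 1% of" total BSA, so two palms are at most 2%.
- Section 6.1: "1 FTU covers approximately 286 cm² (approximately 1.5% BSA", at about 2 mg/cm², with a cap of about 20% BSA.
- Section 6.1: twice daily except on Day 28, so 27 × 2 + 1 = 55 applications.

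**3. Amount applied, two fully involved palms (upper bound)**

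- FTUs per application: 2 / 1.5 = 1.33. For one palm: 1 / 1.5 = 0.67.
- Total BSA implied by the FTU figure: 286 / 0.015 = 19,067 cm².
- Palm area: 2% × 19,067 = 381 cm².
- Gel per application: 381.3 × 2 = 763 mg. Over 55 applications: about 42 g.
- If total BSA is instead assumed to lie between 15,000 and 22,000 cm², the difference per application is 600 to 880 mg.
- Share of the cap: 2 / 20 = 10%. Share of a participant's lesions at 5% total BSA: 2 / 5 = 40%.

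The cap limits the difference. Let A be the treatable area outside the palms, in % BSA. The two instructions give min(A + 2, 20) and min(A, 20). They differ by 2 points up to A = 18, by 20 − A from there, and by nothing at A = 20.

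**4. The 80% ratio in Section 7.5**

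Let T be total BSA and p the palm involvement, both in % BSA, with palms the only untreated lesions. If palms count as untreated, the ratio is (T − p) / T, which is below 0.80 when T < p / 0.2.

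- Two palms (p = 2): below 80% when T is under 10%.
- One palm (p = 1): below 80% when T is under 5%.
- With p = 2: T = 5% gives 60%, 8% gives 75%, 10% gives 80% and 20% gives 90%.

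If palms count as treated, the ratio is 100% at every T.

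**The case against.** The strongest reply is that this is a local wording gap with a small effect. The exclusion of palms appears in several places. The only BSA row in Table 2, the schedule to which Section 7.5 sends the reader for treated-area BSA, is headed as excluding palms. Participants are trained on Day 1 and reminded at each later visit. A Pharmacy Manual, not available here, may add guidance. All arms follow the same text under blinding, so the ambiguity is not tied to treatment. Application rate, coverage and cap are all stated as approximate. Much of this stands and limits the size of the point. It does not remove the conflict, because Section 6.1 is the application instruction itself and lists its exceptions without palms.

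Three stronger readings are tempting, and the documents do not support them.

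- A reader might infer from the hand-washing rule in Section 5.4 that palms are meant to be treated: "If there are lesions on the hands, participants should abstain from washing their hands within 2 hours following each treatment application". The backs of the hands are also hands, so this rule, and its counterpart in Section 6.1, fits either list. Section 5.4 does not conflict and needs no change.
- A reader might infer that a participant with 8% BSA and both palms involved has a ratio of 75% or 100% with equal textual support. The numerator, the intended area, is not defined, and its sentence directly follows the eligibility BSA that excludes palms. Read in that light, the 100% branch may not arise. The example also needs both palms fully involved and no other untreated lesions.
- A reader might infer that sites will treat the same participant differently, or that the primary comparison is biased. The text supports only that practice may differ, and nothing ties the difference to an arm.

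**Conclusion.** Wrong as written: an internal contradiction in current text, not a matter of design preference. A palm lesion receives gel under Section 6.1 and the FTU sentences of Section 7.5, and is barred from it under footnote g. The lists also differ on new sole lesions.

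The size is modest. The upper bound of 2% BSA, about 1.3 FTUs per application and one tenth of the cap, assumes both palms fully involved and other treated lesions at or below 18% BSA. It is smaller for partial involvement or one palm. It applies only to participants with palm lesions, whose number the documents do not give.

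An effect on the 80% ratio is possible but conditional: palms must be counted as untreated, be fully involved on both sides and be the only untreated lesions, with total BSA under 10%. Where it occurs, it could change Day 1 eligibility and so membership of the modified intent-to-treat set. The primary endpoint formula, alpha and sample size do not depend on this point.

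**What to change.** Reconcile Table 2 footnote g, Section 6.1, Section 7.5 and the SAP copy of the footnote to a single list of untreated sites that states the position for both palms and soles. Use that list for the treated-area BSA, for the FTU calculation and to define the intended area in the 80% ratio. Which sites belong on the list is for the sponsor to decide, and no position is taken here. The cost is protocol and SAP wording plus a clarification to sites, with no change to the sample size or the analysis model.
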